5.3 Drug supply

The pharmacist shall take responsibility for and shall take all steps to maintain appropriate records and ensure appropriate supply, storage, handling, distribution and usage of investigational product in accordance with the protocol and any applicable laws and regulations.

5.3.1 Placebo

Placebo for this trial will not be provided by MSD but will be provided by the Investigational sites and prepared by the local unblinded pharmacist.

5.3.2 Pembrolizumab

Pembrolizumab will be provided by MSD.

5.3.2.1 Initial drug supply

Refer to Pharmacy Manual.

5.3.2.2 Drug resupply by IVRS

Refer to the IVRS Manual.

5.3.3 Packaging, labeling, handling and storage

5.3.3.1 Packaging

Packaging and labeling of Pembrolizumab and placebo will be in accordance with Good Manufacturing Practice (GMP) for clinical trials.

5.3.3.2 Labeling

Pembrolizumab will be affixed with a clinical label in accordance with regulatory requirements.

5.3.3.3 Dosage and Administration

Pembrolizumab will be provided by MSD in vials of 50 mg lyophilized powder or in 100 mg liquid vials.

Details on the infusion preparation and administration are provided in the Pharmacy Manual.

5.3.3.4 Storage

Investigational product must be stored in a secure area according to local regulations. It is the responsibility of the Investigator to ensure that investigational product is only dispensed to study subjects. The investigational product must be dispensed only from official study sites by authorized personnel according to local regulations.

The pharmacist must ensure that the investigational product is stored in accordance with the environmental conditions (temperature, light and humidity) as determined by the Sponsor and defined in the Investigator Brochure.

Clinical supplies may not be used for any purpose other than that stated in the protocol.

5.3.4 Drug accountability

The pharmacist is responsible for investigational product accountability, reconciliation, and record maintenance. In accordance with all applicable regulatory requirements, the investigator or designated site staff must maintain investigational product accountability records throughout the course of the study. This person(s) will document the amount of investigational product dispensed and/or administered to study patients, the amount returned, and the amount received from and returned to MSD, when applicable.

5.3.5 Return of investigational product

The pharmacist is responsible for keeping accurate records of the clinical supplies received from the Sponsor or designee, the amount dispensed and returned and the amount remaining at the conclusion of the trial.

For all trial sites, the local country Sponsor personnel or designee will provide appropriate documentation that must be completed for drug accountability and return.

5.3.6 Destruction of investigational product

The pharmacist is responsible for keeping accurate records of the clinical supplies received from the Sponsor or designee, the amount dispensed to and returned by the patients and the amount remaining at the conclusion of the trial. For all trial sites, the local country Sponsor personnel or designee will provide appropriate documentation that must be completed for drug accountability and return, or local discard and destruction if appropriate. Where local discard and destruction is appropriate, the pharmacist is responsible for ensuring that a local discard/destruction procedure is documented. Unused clinical supplies can only be destroyed after being inspected and reconciled by the responsible study monitor.

5.3.7 Standard Policies

Trial site personnel will have access to a central electronic randomization system (IVRS) to allocate patients, to assign treatment to patients and to manage the distribution of clinical supplies. Each person accessing the IVRS must be assigned an individual unique PIN. They must use only their assigned PIN to access the system, and they must not share their assigned PIN with anyone.

5.4 Treatment schedule

Pembrolizumab/Placebo at a dose of 200 mg, administered intravenously (IV), every 3 weeks, for a total of 18 infusions, approximately one year.

Note: if visits are missed and/or delayed treatment will continue beyond 1 year in order to complete 18 infusions.

5.5 Treatment duration

In both arms, treatment will be administered for a maximum of 18 infusions for approximately one year, unless one of the withdrawal criteria applies (see Section 5.6). In case of delay in scheduled administration, the treatment can continue beyond 1 year in order to complete the 18 infusions.

5.6 Subject Withdrawal/Discontinuation Criteria

Subjects may withdraw consent at any time for any reason or discontinue treatment.

In this trial, a subject may discontinue from study treatment for the reason outlined below but will remain in the trial for follow up as outlined in Section 6.7, as long as the subject does not withdraw consent. Discontinuation from study treatment is permanent. Once a subject has discontinued study treatment for the reason outlined below, he/she shall not be allowed to begin study treatment again (This is distinct and different from infusion / treatment delays required due to adverse events. For guidelines for management of toxicity and schedule modification and supportive care guidelines please refer to [Appendix G](#) and [Appendix H](#)). A subject should stop the study treatment (but should be encouraged to continue to be monitored/followed-up in the trial) for any of the following reasons:

- ◆ The subject or legal representative (such as legal guardian) withdraws consent;
- ◆ Disease recurrence by RECIST version 1.1;

- ◆ Unacceptable adverse events;
- ◆ The subject's treatment assignment has been unblinded by the investigator, MSD subsidiary, or through the emergency unblinding call center.
- ◆ Any progression or recurrence of any malignancy, or any occurrence of another malignancy that require active treatment;
- ◆ Inter-current illness (including second malignancy) that, in the opinion of the investigator, warrants the patient's withdrawal from study treatment;
- ◆ Any study intervention-related toxicity specified as a reason for permanent discontinuation as defined in the guidelines for dose modification due to AE in [Appendix G](#) and [Appendix H](#).
- ◆ Investigator's decision to withdraw the subject;
- ◆ The participant has a medical condition or personal circumstance which, in the opinion of the investigator and/or Sponsor, placed the participant at unnecessary risk from continued administration of study intervention.
- ◆ The subject has a positive pregnancy test or is pregnant;
- ◆ Noncompliance with trial study treatment or procedure requirements;
- ◆ Administrative reasons.

After the end of treatment, each subject will be followed for a minimum of 30 days for adverse event monitoring (serious adverse events). Events of Clinical Interests (ECIs) will be collected for up to 90 days following cessation of treatment or 30 days following cessation of treatment if the subject initiates new anticancer therapy. Subjects will have post-treatment follow-up specified in Section [6.7](#).

5.7 Management of toxicity

For management of toxicity and supportive care guidelines please refer to [Appendix G](#) and [Appendix H](#).

5.8 Concomitant medications

All treatments that the Investigator considers necessary for a patient's welfare may be administered at the discretion of the Investigator in keeping with the community standards of medical care. All concomitant medication will be recorded on the case report form (CRF) including all prescription, over-the-counter (OTC), herbal supplements, and IV medications and fluids. If changes occur during the study period, documentation of drug dosage, frequency, route, and date will also be included on the CRF.

All concomitant medications received within 30 days before the first infusion of study treatment and 30 days after the last infusion of study treatment must be recorded.

5.8.1 Prohibited medications

- ◆ Any concurrent anti-cancer treatment (surgery, radiotherapy, systemic therapy);
- ◆ Any investigational agents;

- ◆ Immunosuppressive agents (except for patients treated for irAE);
- ◆ Immune-modulating agents
- ◆ Chronic systemic corticosteroids, with equivalents of more than 7.5mg of prednisone (except for patients which during the study developed endocrinopathies requiring stable doses of hormone replacement therapy such as hydrocortisone);
- ◆ Steroid premedications for contrast CTs are permissible;
- ◆ Live vaccines within 30 days prior to the first infusion of study therapy and while participating in study. Examples of live vaccines include, but are not limited to, the following: measles, mumps, rubella, chicken pox, yellow fever, rabies, BCG, and typhoid vaccine.

6 Clinical evaluation, laboratory tests and follow-up

6.1 General Considerations

The patient's written informed consent to undergo screening for the clinical trial must be given prior to the performance of any protocol laboratory/imaging tests that are not part of local routine guidelines. Therefore, if a patient had laboratory/imaging tests as part of local routine guidelines (standard of care) prior to signing informed consent, the procedures will be acceptable for screening purposes if they are within the window required by the protocol.

The Trial Flow Charts - Section 6.8 summarize the trial procedures to be performed at each visit. Chest and upper abdomen CT scan to assess disease status are mandatory. PET alone will not be used for the disease assessment.

Cytology and/or histology are mandatory to confirm relapse in solitary or in doubtful lesions. Histological or cytological evidence of recurrence should be attempted in all cases except for brain metastases.

Individual trial procedures are described in detail below. It may be necessary to perform these procedures at unscheduled time points if deemed clinically necessary by the investigator.

Additional evaluations/testing may be deemed necessary by the investigator and or the Sponsor for reasons related to patient safety. In some cases, such evaluation/testing may be potentially sensitive in nature and thus local regulations may require that additional informed consent be obtained from the patient. In these cases, such evaluations/testing will be performed in accordance with those regulations.

6.1.1 Subject Identification Card

All patients will be given a Subject Identification Card identifying them as participants in a research trial. The card will contain trial site contact information (including direct telephone numbers) to be utilized in the event of an emergency. The investigator or qualified designee will provide the patient with a Subject Identification Card immediately after the patient provides written informed consent.

The subject identification card also contains contact information for the emergency unblinding call center so that a health care provider can obtain information about trial medication/vaccination in emergency situations where the investigator is not available.

6.2 Before treatment start

- ◆ Eligibility criteria (see Section 3.1);

A specific informed consent ('Registration') has been prepared to send the tumor sample for the PD-L1 status and must be signed by the patient before shipment of the tumor. This is mandatory. At the same time the consent for the optional Translational Research (TR) ('Biomedical Research') will be presented to the patient (see Section 6.5). This consent must be signed before any additional TR samples are collected. It is recommended patients sign the TR ICF along with Registration to collect Step 1 samples. However, the patient can reconsider taking part in the optional TR at a later stage during the trial. The Main informed consent will be signed during the referral period after the surgery if no adjuvant chemotherapy is foreseen or at the end of standard adjuvant chemotherapy. This consent must be signed before any additional TR samples are collected.

- ◆ Whole blood for germline (20 mL) and serum (20 mL) (during Step1)
- ◆ Whole blood for correlative DNA, whole blood for correlative RNA, PBMC (for selected sites in Spain, France and Switzerland only, during Step 3)

6.2.1 Within 12 weeks prior to randomization

The patient's written informed consent ('Main Study') to undergo screening for the clinical trial must be given prior to the performance of any protocol laboratory/imaging tests (that are not part of local routine guidelines) and collection of HQRoL,.

Upon confirmation of the PD-L1 status and ('Main Study') written informed consent, the following exams will be performed during the screening phase (maximum of 12 weeks from ICF signature until the randomization) and results must be known before randomization:

- ◆ Eligibility criteria (see Section 3.3);
- ◆ Demographics, medical history, height and smoking status;
- ◆ HIV, HBV, HCV serology (Active Hepatitis B is defined as a known positive HBsAg result. Active; active Hepatitis C is defined by a known positive Hep C Ab result and known quantitative HCV RNA results greater than the lower limits of detection of the assay) if clinically indicated according to the local investigator;
- ◆ Physical examination (including heart rate, blood pressure, weight and temperature);
- ◆ ECOG performance status (see Appendix C);
- ◆ Urinalysis (specific gravity, pH, proteins, glucose, blood using a dipstick; elements and microscopic examination if needed);
- ◆ Thyroid function: TSH; in case of elevated TSH to add free T3 and T4;
- ◆ Cardiac function: 12-lead ECG;
- ◆ Disease evaluation : the following imaging work up must be performed:

- ◆ Contrast-enhanced chest and upper abdomen CT scan;
- ◆ Contrast-enhanced brain CT scan or MRI;
- ◆ Concomitant medications assessment;
- ◆ Adverse event assessment;
- ◆ HRQoL evaluations : EORTC QLQ-C30 version 3, EORTC QLQ-LC13 and EQ-5D;

Please refer to [Table 4](#) in Section [6.8.1](#).

6.2.2 Within 10 days prior to treatment initiation

- ◆ Hematology: white blood cell count (WBC), absolute neutrophils count (ANC), lymphocytes, eosinophils, basophils, monocytes, red blood cell count (RBC), hemoglobin (Hgb), haematocrit (Hct), platelets;
- ◆ Serum chemistry: creatinine, urea or blood urea nitrogen (BUN), total bilirubin*, AST, ALT, alkaline phosphatase, LDH, tot proteins, potassium (K), sodium (Na), calcium (Ca), bicarbonate (HCO₃) (HCO₃ testing could be optional in countries where testing is not standard of care), albumin and glucose.

* If total bilirubin levels >1.5xULN, direct bilirubin must be collected.

Please refer to [Table 4](#) in Section [6.8.1](#).

Note: hematology and serum chemistry are to be repeated if performed more than 10 days prior to the first infusion of study treatment.

6.2.3 Within 72 hours prior to treatment initiation

- ◆ Pregnancy test: serum (or urine) beta HCG in fertile female study participants. This pregnancy test is to be renewed/repeated during protocol treatment at least monthly or more frequently if required by national regulations/institution guidelines

Note: the pregnancy test is to be repeated if performed more than 72 hours prior to the first infusion of study treatment.

6.2.4 Within 24 hours prior to treatment initiation

- ◆ Pharmacokinetics: one blood sample of 3.5 mL;
- ◆ Anti-pembrolizumab antibody (ADA): one blood sample of 6 mL;
- ◆ Additional PK and ADA samples will be collected at subsequent infusions outlined in study;

Please refer to in Section [6.8.3](#).

6.3 During treatment

Pregnancy test: serum (or urine) beta HCG in fertile female study participants. This pregnancy test is to be renewed/repeated during protocol treatment at least monthly or more frequently if required by national regulations/institution guidelines.

Infusion schedule

1) Normal schedule

Window of administration is up to 3 days before or after the scheduled day of each infusion, due to administrative reasons, except for infusion 1 where the window is + 7 days from randomization.

2) Delayed infusions

Definition of **delayed** infusion: an infusion is considered as delayed if administration occurs at least 3 days after the theoretical date, but less than 10 days after the theoretical date. Future infusion dates should follow every 3 weeks, calculated from the actual date of administration of the delayed infusion. If **infusion is delayed** (e.g. patient on holiday, adverse events, hospitalized, etc) the site must:

- ◆ Complete all protocol required laboratory tests, physical exam, adverse events assessments, concomitant medication assessments and HRQoL assessments within the required window prior to the new date of infusion.
- ◆ Follow calendar days for imaging assessment and not adjust for delays. The reference date for imaging scans must be the date of the first infusion (infusion 1).

3) Missed infusions

Definition of **missed** infusions: an infusion is considered as missed if administration would occur more than 10 days after the theoretical date. In this case, no infusion is given. The next infusion should occur as soon as the cause of the missed infusion is resolved and not delayed until the next scheduled infusion. Future infusion dates should follow every 3 weeks, calculated from the actual date of administration of the delayed infusion.

If **infusion administration is missed** (e.g. toxicity, delay greater than 10 days, etc), the site must:

[figure not shown]
- ◆ Complete all protocol required laboratory tests, physical exam, adverse events assessments, concomitant medication assessments and HRQoL assessments within the required window prior to the **missed** date of infusion administration. If a visit did not occur, documentation is required (see CRF completion guidelines).
- ◆ Follow calendar days for imaging assessment and do not adjust for delays. The reference date for imaging scans must be the date of the first infusion (infusion 1).

Due to missed infusions, completion of 18 infusions will extend beyond 1 year and must be assessed as per protocol Section 6.3.

The visits for evaluations described below refer to study drug administrations.

It is therefore expected that results of laboratory (hematology, serum chemistry, thyroid, urinalysis) and imaging results are available prior to study drug administrations and within required timelines every 3 weeks (+/- 3 days), every 6 weeks (+/- 3 days) and every 12 weeks (+/- 3 days or +/- 2 weeks) depending on the type of evaluation.

Figure 2: Overview schedule of test/exams

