7.1.1 Assessment of tumor lesions

7.1.1.1 Methods of assessment

The determination of patient's eligibility and the determination of tumor progression will be done by local principal investigator based on the schedule outlined for disease evaluation in [Table 4](#). Imaging needs to be based on calendar and not adjusted for delays in treatment. The images will be collected by the central vendor for quality assurance and future central review. The process for image collection and transmission to the central vendor can be found in the Site Imaging Manual. The same method of assessment and the same technique should be used to identify and report lesion during follow-up. Assessments should be identified on a calendar schedule and should not be affected by delays in therapy, which may be treatment arm dependent. At the time of occurrence of a lesion, their actual measurements should be recorded on the CRF even when very small (e.g. 2 mm). For lesions which fragment/split add together the longest diameters of the fragmented portions; for lesions which coalesce, measure the maximal longest diameter for the "merged lesion".

- ◆ **CT or MRI** are mandatory to establish recurrence. Conventional CT with i.v. contrast with contiguous cuts of 10 mm or less slice thickness is the best currently available and reproducible method to assess and measure lesions. If CT IV contrast is contraindicated, a non-contrast CT is recommended over MRI for radiographic evaluation of the chest. MRI is also acceptable in certain situations (e.g. for body scans). If a patient cannot have a CT scan or MRI with contrast during the screening phase, the patient is not eligible. A CT scan or MRI without contrast is acceptable during the treatment and follow-up phases if the patient develops a medical problem that precludes the use of contrast agents. Performance of a non-contrast CT scan or MRI will be reported as a deviation to the protocol during medical review.
- ◆ **PET** alone will not be considered for the disease assessment. Complementary CT/MRI or biopsy must be performed in such cases.
- ◆ **Cytology or Histology** are mandatory to confirm recurrence in solitary or in doubtful lesions. Histological or cytological evidence of recurrence should be attempted in all cases except for brain metastases.

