10.4 Study design

HRQoL questionnaires must be filled out at the hospital when patients come for a scheduled visit according to the EORTC "Guidelines for administration of questionnaires" (see [Appendix E](#)). The pre-treatment questionnaires must be filled in within 12 weeks before randomization. Subsequent questionnaires are filled in every 12 weeks, during the 1st year after randomization; every 6 months during the 2nd year and then yearly until year 5. HRQoL data must be collected regardless of the patient's progression status; no further collection is required beyond the fifth year.

The assessment schedule is chosen to coincide as much as possible with the disease assessment schedule in order to maximize compliance. The week 74 assessment therefore corresponds to the last scheduled on-treatment disease assessment visit at week 48 plus 26 weeks (= 6 months). Subsequent assessments occur at 26 weeks (= 6 months) intervals. Collection beyond year 5 is not deemed necessary as most symptoms will have stabilized by then and the available patient population will have decreased due to attrition.

Master copies of the HRQoL questionnaires will be sent to the institutions. Additional copies or translations can be provided upon request via the EORTC contact person. The clinical report forms will include a question whether the HRQoL forms have been filled in, and if not, the reason why. The questionnaire will be handed out to the patients by the investigator or a study nurse prior to seeing the doctor for clinical evaluations. The patient should complete the questionnaires by her/himself in her/his own language during the visit to the outpatient clinic as completely and accurately as possible. In the event telephone transcript is utilized, the designated study staff should capture the patient's responses on the HRQoL forms. It is recommended that a key person (e.g. research nurse) at each center should be responsible for questionnaire data collection in order to optimize the compliance of the patient and to ensure the completeness of the data.

During the study, compliance with completing questionnaires will be investigated at each time point and reviewed twice a year.

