10.4.1 HRQoL schedule

The time windows for eligible HRQoL including EQ-5D assessments will be as follows:

Assessment	Time window
Baseline	Can be completed before or on the day of randomization itself but no earlier than 12 weeks before.
Week 12	Can be completed at week 12 (+/-3 weeks) after randomization.
Week 24	Can be completed at week 24 (+/-3 weeks) after randomization.
Week 36	Can be completed at week 36 (+/-3 weeks) after randomization.
Week 48	Can be completed at week 48 (+/-3 weeks) after randomization.
Week 74	Can be completed at week 74 (+/-4 weeks) after randomization.
Week 100	Can be completed at week 100 (+/-4 weeks) after randomization.
Week 152	Can be completed at week 152 (+/-4 weeks) after randomization.
Week 204	Can be completed at week 204 (+/-4 weeks) after randomization.
Week 256	Can be completed at week 256 (+/-4 weeks) after randomization.

 HRQoL data must be collected regardless of the patient's progression status.

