10.5 Statistical considerations

The key exploratory HRQoL endpoint relevant for this study is the global health/QoL scale. The following sub-scales and single items will be considered as supportive exploratory HRQoL endpoints: pain, fatigue, appetite loss, shortness of breath, cough, chest pain and dyspnea symptom scales. The other available scales will be classified as "other" exploratory analyses; the financial difficulties scale will not be presented.

The global health/QoL scale will be used as primary outcome of interest for this study. A difference of 10 points on the 100-point QLQ-C30 scale either within a patient or between the two arms will be considered as clinically relevant [Ref. 78]. The standard deviation of this scale is approximately 20 points. With the 2-sided alpha set at 5% and a power of 80% to detect a difference of 10 points (effect size of 0.5), a minimum of 128 patients (64 per treatment arm) is required. For an effect size of 0.75 (difference of 15 points), 56 patients (28 per treatment arm) are required. Therefore, this study is sufficiently powered to detect differences in HRQoL.

Data will be scored according to the algorithm described in the EORTC scoring manual. All scales and single items are scored on categorical scales and linearly converted to 0-100 scales.

Changes in HRQoL scores from baseline per time point will be evaluated by classifying them according to the 10 point change threshold into 3 categories: improved/stable/deteriorated. Patients without a valid HRQoL outcome at a certain time will be considered as having deteriorated at that time. For each patient the proportion of assessments spent in a deteriorated state will be calculated and compared between treatment arms using a non-parametric rank order test in the intent-to-treat population of the whole population and in the PD-L1 strong positive subgroup.

In order to assess the robustness of the results, the following sensitivity analyses will be performed:

- ◆ a clinical relevant threshold of 5 and 15 points will be used and patients without a valid HRQoL score will be classified according to the reported reason for non-compliance.
- ◆ If adequate compliance available, patients will be classified on valid HRQoL score received after treatment discontinuation only.
- ◆ The area-under-the-curve (AUC) will be calculated for each patient based on the global health/QoL scores. Missing values will be considered as 0.

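### HRQoL forms have two clocks: Section 6.3 lets them move with infusions, 10.4.1 counts windows from randomization, so accumulated delays could turn completed forms into deteriorations

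*Combined protocol and SAP*

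**What the plan says.** **Text that lets forms move with infusions**

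- Section 6.3, item 2 (delayed infusions): "an infusion is considered as delayed if administration occurs at least 3 days after the theoretical date, but less than 10 days after". The site must then complete "concomitant medication assessments and HRQoL assessments within the required window prior to the new date of infusion". Later infusions follow every 3 weeks from the actual date. Only imaging is told to keep to calendar days.
- Section 6.3, after item 3: "The visits for evaluations described below refer to study drug administrations".
- Table 4 lists HRQoL in the 12-weekly ±3-day column with urinalysis, not in the 12-weekly ±2-week column used for imaging.
- Section 10.4 wants forms completed at the hospital at a scheduled visit. Appendix E wants them completed before any treatment given that day.

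**Text that holds forms to a calendar**

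- Section 6.3, item 3 (missed infusions): "an infusion is considered as missed if administration would occur more than 10 days after the theoretical date". Here the HRQoL form belongs before the missed date, not the new one.
- Section 6.3.3 and Table 4 footnote 7: every 12 weeks ±3 weeks in the first year, counted from day 1 of infusion 1.
- Section 10.4: "The assessment schedule is chosen to coincide as much as possible with the disease assessment schedule in order to maximize compliance". Disease assessment is calendar-based.
- Section 10.4.1 lists the windows for eligible forms, for example "Can be completed at week 12 (+/-3 weeks) after randomization".

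**Scoring**

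Section 10.5, main analysis: "Patients without a valid HRQoL outcome at a certain time will be considered as having deteriorated at that time". Each patient's proportion of assessments in a deteriorated state is then compared between arms.

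**The concern.** A site that follows the infusion-linked text can collect a completed form that 10.4.1 does not list as eligible. If that form is then treated as not valid, 10.5 turns a scheduling matter into a recorded deterioration.

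This is more than noise if delays differ by arm. Section 7.1.1.1 gives that reason for keeping tumour assessments on a calendar: they "should not be affected by delays in therapy, which may be treatment arm dependent". HRQoL has no equivalent safeguard. Appendix G withholds pembrolizumab for several immune-related events and allows resumption after a steroid taper of at least 4 weeks, so an excess of holds on pembrolizumab is plausible. Section 10.2 expects no significant HRQoL decrement on pembrolizumab, and an artefact in this direction would count against that expectation.

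**Working it through.** **The plan's own HRQoL figure.** For 10 points, SD 20, two-sided 5% and 80% power, the normal approximation gives 63 per arm and the t-test version 63.8, so 64 per arm, or 128 in total, as stated in 10.5. For 15 points it gives 28 per arm, also as stated. The point here rests on window widths, not on these numbers.

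**Inputs**

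- Windows (10.4.1): weeks 12, 24, 36 and 48, each ±3 weeks, which is 9–15, 21–27, 33–39 and 45–51. Then weeks 74, 100, 152, 204 and 256, each ±4 weeks. That makes nine post-baseline assessments.
- Lag from randomization to infusion 1 (4.1.3, 6.3): 0 to 7 days.
- One delayed infusion (6.3): at least 3 and less than 10 days, so at most 9 whole days.
- Follow-up visits (6.7.2) are referenced to day 1 of infusion 1, so forms from week 74 do not move with holds.

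**Step 1: shift needed to leave a window.** Offset = lag + accumulated shift, and the form is out when the offset exceeds 21 days. With lag 0 the smallest such shift is 22 days. With lag 7 it is 15 days.

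**Step 2: the delayed-infusion rule.**

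| Maximal delays | Offset, lag 0 | Offset, lag 7 |
|---|---|---|
| 1 | 9 (in) | 9 + 7 = 16 (in) |
| 2 | 18 (in) | 18 + 7 = 25 (out) |
| 3 | 27 (out) | 27 + 7 = 34 (out) |

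Two maximal delays breach the window only if the lag is at least 4 days (18 + 4 = 22).

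**Step 3: the missed-infusion rule.** A hold of more than 10 days falls under item 3, so a form due at that infusion stays at the missed date. Later infusions are still re-anchored. Later forms drift only if the site ties them to infusions.

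**Step 4: forms lost under the infusion-linked reading, lag 0.** For a shift of more than 3 and less than 9 weeks:

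| Shift occurs before | Windows left empty |
|---|---|
| week 12 | 4 of 9 |
| week 24 | 3 of 9 |
| week 36 | 2 of 9 |
| week 48 | 1 of 9 |

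For example, a 5-week shift before week 12 moves the forms to weeks 17, 29, 41 and 53. None lies in 9–15, 21–27, 33–39 or 45–51, and the next window opens at week 70. Where the form due at week 12 belongs to a missed infusion, item 3 probably keeps it in place, leaving 3 of 9. A shift of 9 to 12 weeks empties only one window, because shifted forms land in the following one.

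**Step 5: the calendar reading.** If forms follow the calendar from infusion 1, the systematic offset is at most 7 days against 21, and holds put 0 of 9 windows out of range.

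**Step 6: effect on the score (illustration).** The documents give no hold rates, so the excess of such holds in one arm is assumed. The addition to that arm's mean proportion deteriorated is excess × forms lost ÷ 9. This is an upper limit, because it supposes that the lost forms would otherwise not have shown deterioration.

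| Assumed excess (percentage points) | 1 of 9 lost | 4 of 9 lost |
|---|---|---|
| 2 | 0.2 | 0.9 |
| 5 | 0.6 | 2.2 |
| 10 | 1.1 | 4.4 |
| 20 | 2.2 | 8.9 |

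**The case against.** The strongest reply is that the specific HRQoL rule is already calendar-based. Sections 6.3.3 and 6.7.2.2 and Table 4 footnote 7 all give 12-weekly forms from the first infusion. Item 2 itself asks for completion inside the required window, which can be read as that same ±3-week window. The sentence linking visits to drug administrations is weak evidence, since the next sentence includes imaging, which is expressly not adjusted, and does not name HRQoL. This shows that the calendar reading is available. It does not remove the other reading, because item 2, the re-anchoring of infusions and the Table 4 column all point the other way, and only imaging is told not to adjust.

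A reader might infer that a single toxicity hold makes every year-1 form invalid and scored as deteriorated, mainly on pembrolizumab. The documents do not support that:

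- A hold of more than 10 days falls under the missed rule, which keeps the form due then at the missed date. One delay cannot breach the window.
- The Appendix G paragraph allowing interruptions of up to 12 weeks concerns events not related to study therapy. It cannot be used to size an arm-dependent effect.
- No section says that a completed out-of-window form is discarded. That is inferred from the words *eligible* (10.4.1) and *valid* (10.5).
- No delay or hold rates by arm are given.

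The plan also has partial safeguards. One sensitivity analysis in 10.5 reclassifies by the reported reason for non-compliance, and 10.5.1 examines the compliance mechanism. These may not catch the problem: under 10.4 the CRF asks for a reason only when forms were not filled in, so a completed late form would have none. The area-under-the-curve analysis sets missing values to 0, which penalizes in the same direction.

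The difference between randomization and infusion 1 as anchor is at most 7 days and harmless alone. It matters only by lowering the shift needed from 22 to 15 days.

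**Conclusion.** The inconsistency stands and is worth correcting, with a limited and conditional consequence. Completed forms are at risk only if (a) the site ties them to infusions, (b) the accumulated shift reaches 22 days, or 15 with the full lag, and (c) out-of-window forms are treated as not valid. The loss is then at most 4 of 9 post-baseline forms, taking all nine scheduled assessments as the denominator. Bias between arms also needs an imbalance in delays. Section 7.1.1.1 allows for this, and it is plausibly more frequent on pembrolizumab, but the documents do not quantify it. HRQoL is exploratory, and the primary and secondary endpoints are untouched.

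**What to change.** 1. In Section 6.3, items 2 and 3, move HRQoL out of the list tied to infusion dates and into the imaging bullet, so that it follows calendar days and is not adjusted for delayed or missed infusions.
2. Use one anchor and one window in 6.3.3, Table 4 (column and footnote 7), 6.7.2.2 and 10.4.1.
3. In 10.5, specify before unblinding that a completed out-of-window form is assigned to the nearest scheduled time point before the rule that counts missing as deteriorated is applied. This also covers forms already collected.

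The cost is a wording change and one programming rule. Some forms will be completed at the scan visit instead of an infusion visit, which fits the stated aim in 10.4 of matching the disease assessment schedule.
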